## **10 FURTHER ANALYSIS**

If the error in stratification by gestational age results in an imbalance in gestational age between the treatment groups, evaluation of secondary outcomes by treatment group will be done using gestational age as a covariate if specified analyses can adjust for this factor. To have reasonable results, each cell count needs to be 5 or greater.

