7.3.16 Further analysis

Prior to the second season of enrollment, randomization was stratified by gestational age (<20 weeks versus 20-34 weeks) and by site. Stratification by gestational age was removed from Version 2.1 due to an error in the randomization schema noted after the first season. The overall randomization to RIV4 vs IIV4 was maintained but the gestational age stratification was unbalanced due to the error.

If the error in stratification by gestational age results in an imbalance in gestational age between the treatment groups, evaluation of secondary outcomes by treatment group will be done using gestational age as a covariate if specified analyses can adjust for this factor. To have reasonable results, each cell count needs to be 5 or greater.

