#### **4.4 Randomization**

Participants will be randomized (1:1) to receive either RIV4 (Flublok® quadrivalent recombinant influenza vaccine) or IIV4 (quadrivalent inactivated influenza vaccine) using a permuted block randomization scheme stratified by study site (Duke, Cincinnati, Boston). The project statistician will generate permuted block randomization schemes which will be uploaded to REDCap. The randomization schedule will not be available to the study staff, so the next randomization allocation will not be known before randomization occurs. Following confirmation of study eligibility criteria during Visit 1, participant randomization will be through REDCap with treatment allocation recorded on the case report form (CRF).

In the event that REDCap is unavailable, manual randomization will occur through the use of envelopes. The project statistician will prepare 20 envelopes per gestational age group per site (total of 40 per site) that will use the same randomization strategy as the primary scheme embedded in REDCap. When an unblinded team member is informed of the gestational age group, he/she will pull the next envelope in order. In order to capture the allocation per subject, a separate form in REDCap will be used by the unblinded personnel to add the assignment. A log will need to be kept at the site capturing these instances.

We had planned to have gestational age as a stratification factor for randomization (<20 weeks,  $\geq$  20 weeks). Unfortunately, the setup in REDCap only drew from the <20 weeks randomization block. The benefits for randomization have been maintained, and we will evaluate secondary outcomes by site and gestational age to determine if specified analyses can adjust for this factor. The cell counts need to be 5 or greater to have reasonable results.

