#### **5.2 Analytic Issues**

There are three study sites participating in the study and analysis of the primary objective will be stratified by site (Duke, Boston, Cincinnati) to account for this unit of randomization. All objectives will be stratified by site when applicable. There is one primary objective being evaluated, using a noninferiority hypothesis at the one-sided alpha 0.025 level. Otherwise, the alpha level will be set at two-sided alpha 0.05 for the secondary objectives and all exploratory objectives.

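### Gestational age, a stratification factor lost to the REDCap error, has no planned adjusted analysis for the primary composite, and adjustment of secondary outcomes waits on an observed imbalance

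*SAP*

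**What the plan says.** - **Design.** Protocol 7.3.16 records that before the second season "randomization was stratified by gestational age (<20 weeks versus 20-34 weeks) and by site". SAP 4.4 explains that REDCap drew only from the list for women below 20 weeks. GA stratification was then dropped.
- **Primary.** SAP 5.2: "analysis of the primary objective will be stratified by site (Duke, Boston, Cincinnati) to account for this unit of randomization". SAP 8.1 and Protocol 7.3.3 accordingly use a site-stratified Newcombe interval with CMH weights. The only sensitivity analysis of the primary (SAP 9) regroups women by vaccine received.
- **Secondary outcomes.** SAP 10 opens with a condition, "If the error in stratification by gestational age results in an imbalance in gestational age between the treatment groups", and continues "evaluation of secondary outcomes by treatment group will be done using gestational age as a covariate if specified analyses can adjust for this factor". Protocol 7.3.16 has the same rule and adds "To have reasonable results, each cell count needs to be 5 or greater".
- **SAP 4.4** also covers secondary outcomes only: "we will evaluate secondary outcomes by site and gestational age to determine if specified analyses can adjust for this factor". It repeats the threshold ("The cell counts need to be 5 or greater to have reasonable results") but does not mention imbalance.
- **Elsewhere.** GA at vaccination is tabulated by arm (SAP 7.1). The spontaneous abortion comparison (SO3) is restricted to women vaccinated before 20 weeks (SAP 8.2).

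**The concern.** The plan responds to the lost stratum for secondary outcomes but not for the endpoint that decides the trial. Yet the definitions in SAP 8.1 tie GA at vaccination to the composite. Spontaneous abortion is a loss before 20 weeks, so only women vaccinated before then can have one. A woman vaccinated at 34 weeks has already passed most of the period in which a preterm birth could occur.

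If chance puts more early-gestation women in IIV4 and their risk is higher, the site-only difference leans toward noninferiority. The reverse imbalance costs power. Preterm birth could be GA-adjusted as a secondary outcome, but no planned analysis would give a GA-adjusted difference for the composite.

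For secondary outcomes, whether adjustment happens depends on the observed baseline split and, if cells count events, on outcomes as well.

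**Working it through.** **1. The plan's power figure.** Inputs from SAP 4.3: 204 per arm, 15% in both arms, margin 10 points, one-sided alpha 0.025.
- SE = sqrt(2 × 0.15 × 0.85 / 204) = 3.54 points.
- Power = Φ(0.10/0.0354 − 1.96) = 80.7%, against the stated 81%. The figure reproduces and needs no change.

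**2. Size of a chance imbalance.** The documents give no early share, so 30%, 40% and 50% below 20 weeks are assumed. The SD of the between-arm difference in share, sqrt(2s(1 − s)/204), is 4.54, 4.85 and 4.95 points. An imbalance of at least 1 SD in the harmful direction has probability P(Z > 1) = 16%.

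**3. Shift in the primary difference** (risk gap × imbalance). The gaps are also assumptions.
- 5-point gap: 0.05 × 4.54 to 4.95 = 0.23-0.25 point.
- 10-point gap: 0.10 × 4.54 to 4.95 = 0.45-0.50 point.

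**4. Closed-form effect of a 1-SD imbalance.**
- Error: at a true difference of 10 points (25% v 15%), SE = sqrt((0.25 × 0.75 + 0.15 × 0.85)/204) = 3.93 points, and error = Φ(−1.96 + shift/SE). A 0.25-point shift gives 2.9%; a 0.50-point shift gives 3.3%.
- Power with the imbalance reversed = Φ((0.10 − shift)/0.0354 − 1.96): 78.7% at 0.25 point, 76.6% at 0.50 point.

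**5. Simulation of the planned interval.** Stratified Newcombe with CMH weights, 200,000 trials per scenario, sites assumed 68/68/68 or 102/51/51 per arm. Error is taken at a true difference of 10 points in each GA group, power at zero. Ranges run over early shares and site splits, and over both gaps where none is named.

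| Scenario | Site only | Site × GA |
|---|---|---|
| GA split left to chance: error | 2.5-2.7% | 2.5-2.6% |
| GA split left to chance: power | 80.3-80.6% | 80.0-80.4% |
| 1 SD more early women in IIV4, 5-point gap: error | 2.9-3.0% | 2.5-2.6% |
| Same, 10-point gap: error | 3.3-3.4% | 2.5-2.6% |
| Reversed, 5-point gap: power | 78.3-78.7% | 80.0-80.5% |
| Reversed, 10-point gap: power | 76.5-77.0% | 80.0-80.5% |
| GA unrelated to risk: power | 80.2-80.5% | 79.9-80.2% |

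**6. The conditions on secondary outcomes.**
- Imbalance trigger, under correct randomization: p < 0.05 fires in 5.0-5.3% of trials, a standardized difference above 0.2 in 4.2-4.6%, an absolute difference of 10 points or more in 2.7-4.2%, and a standardized difference above 0.1 in 30-32%.
- Cell rule, preterm birth at an assumed 15%: satisfied in at most 0.14% of trials if cells are events by site, GA and arm; in 91-99.8% if events by GA and arm; in at least 99.9% if cells are participants.
- Cell rule, fetal/neonatal death at an assumed 0.5-2%: event cells by GA and arm almost never pass.

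**The case against.** The case for leaving the plan alone is substantial.

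- **The primary matches the randomization.** Current allocation is stratified by site only, and so is the analysis. A reader might infer that the REDCap error biases the primary. It does not: drawing everyone from one list still randomizes within site, and unconditional error and power barely differ between the two analyses. This stands.
- **The effect is conditional and assumed.** The 2.9-3.4% error needs a harmful 1-SD imbalance plus a risk gap that the documents do not give. Even then the shift is at most 0.5 point, against a standard error of about 3.5. This stands.
- **The secondary outcomes cover every component of the composite**, and these would be GA-adjusted if the trigger fires. True, so the gap is the narrower one of an adjusted risk difference for the composite itself.
- **Two GA groups cannot remove a gradient within 20-34 weeks.** The simulation favours the split because it lets risk vary only between the two groups. If GA were uniform over 6-34 weeks, the split would capture 75% of GA-related risk variance when risk is linear in weeks, 60% when risk falls only after 20 weeks, and 19% when only after 28. This limits the remedy without removing its value.
- **Two further inferences are tempting.** Protocol 7.3.16 says "the gestational age stratification was unbalanced due to the error", which could suggest the trigger is already met. That sentence is about the stratification scheme; whether the arms differ in GA is properly left open in the next paragraph. SAP 4.4 might also seem to contradict SAP 10, but 4.4 can be read as a feasibility check and 10 as the condition for adjusting. Neither is a firm contradiction.

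**Conclusion.** The site-only primary is valid and should remain primary. The point is a cheap gain in robustness. A factor once judged important enough to stratify on, and linked to the composite by the plan's own definitions, has no planned adjusted analysis for that composite; for secondary outcomes the adjustment is triggered by observed data.

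The benefit is protection against chance imbalance, not unconditional power. The size rests on three assumptions: an early share of 30-50%, a risk gap of 5-10 points, and risk that differs only between the two GA groups. The textual part, that GA adjustment is confined to secondary outcomes, needs no assumption.

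That imbalance, cell and the form of GA are undefined is missing detail and a minor wording matter on its own. The trigger frequencies should not be over-read: three of the four candidate definitions fire in 2.7-5.3% of trials, and only the loosest reaches 30%.

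**What to change.** 1. **Primary.** Keep the site-only interval as the decision rule. Beside it, pre-specify a supportive stratified Newcombe/CMH interval over site × GA at vaccination (below 20, 20-34 weeks), reported whatever balance is observed.
2. **SO1 and SO2.** Replace the imbalance trigger with site × GA strata used unconditionally in the exact Mantel-Haenszel test. Do not apply the minimum cell count to that test, which is exact and does not need it.
3. **Align SAP 4.4, SAP 10 and Protocol 7.3.16.** For any covariate models that remain, such as adjustment within SO3, state the form of GA, what a cell contains and the fallback if the rule fails. Say whether SO4 is covered.

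**Cost.** Wording in two documents and one variable already collected. There would be six strata instead of three, averaging 408/6 = 68 women. If GA is unrelated to risk, the supportive interval loses at most about 0.4 point of power. SO2 gains little, because strata without events add no information. A risk gradient within 20-34 weeks would remain.

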## **APPENDIX 1**

### **Major Protocol Violations for Analysis**

1. Major Protocol Violations for Exclusion from Per Protocol Populations:
  - a. Age < 18 years of age at enrollment
  - b. Gestational age >34 weeks at vaccination
  - c. Did not provide written informed consent prior to vaccination
  - d. End of participation in study (e.g. loss to follow-up, early termination/withdrawal) prior to end of pregnancy
  - e. Receipt of the year's influenza vaccine (2019-20 or 2020-21) prior to study enrollment
  - f. Study participation in both 2019-20 and 2020-21 influenza season
  - g. Receipt of live vaccine while participating in this study or receipt of non-study vaccine within 7 days before or during the 8 days post-vaccination period.
  - h. Receipt of experimental drugs or medical device while participating in this study
  - i. Known multi-fetal gestation or fetal congenital anomaly at the time of enrollment, e.g. genetic abnormality or major congenital malformation based on antenatal ultrasound before randomization
2. Major Protocol Violations for Exclusion from Immunogenicity Populations:
  - a. No vaccine received
  - b. No pre- and/or post-vaccination blood draw
  - c. Receipt of any other vaccine between the pre- and post-vaccination blood draws
  - d. New immunosuppression disorders between the pre- and post-vaccination blood draws or receipt of immunosuppressive medication between the pre- and post-vaccination blood draws
  - e. Subject who was inadvertently enrolled and randomized to the study, though they were later learned to have had met the following criteria for study exclusion that would have affected immunogenicity
  - f. Influenza vaccine receipt during the current influenza season prior to study enrollment
  - g. Use of oral, antenatal, or parenteral corticosteroids ( $\geq$  20mg/day prednisone equivalent) or high-dose inhaled glucocorticoid for  $\geq$  14 consecutive days within the preceding 30 days
  - h. Has an active neoplastic disease (excluding non-melanoma skin cancer), a history of any hematologic malignancy, current bleeding disorder, or taking anticoagulants (a daily aspirin is acceptable)
  - i. Has a history of receiving immunoglobulin or other blood product (with exception of Rh immunoglobulin) within the 3 months prior to study vaccination

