4.4 Reasons for and Handling of Withdrawals

The following may be reason for study withdrawal:

- As deemed necessary by the principal investigator (PI).
- Participant withdrawal of consent.
- Loss to follow-up.
- Termination of the study by the sponsor.

Participants may withdraw their consent for study participation at any time and for any reason, without penalty. Participants who withdraw from the study prior to receiving study vaccine will be replaced. Participants who withdraw from the study after receiving vaccine will not be replaced. Every attempt should be made to collect all data specified by the protocol, including collection of pregnancy outcome/safety data via medical record review for participants who request withdrawal from study interventions/procedures.

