5.1.3 Vaccine Supply, Storage, and Administration

In order to ensure adherence to study randomization assignment, licensed RIV4 and IIV4 vaccines will be administered as study procedures. Licensed RIV4 and IIV4 will be

20

purchased for study administration and will be stored at 2° to 8°C in a research-specific medication refrigerator. While research staff maintain daily temperature logs for the medication refrigeration, it is also monitored 24/7 with alarm activation if out of range. Research staff are notified of any alarm activations and have an on-call system in place to report to the research center for further investigation. Flublok® quadrivalent (Sanofi) and quadrivalent Flulaval® (GSK) will be the designated study products.

A single administration of both RIV4 and IIV4 comprises intramuscular delivery of 0.5mL total volume of each vaccine for adults. Unblinded, licensed providers will prepare the RIV4 or IIV4 by using opaque tape to cover the syringe before vaccine administration. Vaccine lot numbers will be recorded in the study accountability log available only to unblinded licensed staff or the investigational pharmacist. Dose and site of vaccine administration will be recorded by unblinded licensed staff. RIV4 and IIV4 will be administered in the deltoid of the patient's preferred arm by an unblinded licensed provider. After administration, used study syringes will be disposed of according to standard operating procedure.

A licensed provider who will be trained on the study protocol, will be present at the time of vaccine administration along with emergency management supplies available for initial treatment of an allergic reaction if needed. Additionally, a blinded post-assessment team will be present to assist study participants following vaccine administration; they will not be in the room at the time of vaccination.

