### **6 ANALYSIS POPULATIONS**

#### **6.1 Modified Intent-to-Treat (mITT):**

The mITT Population includes any participant that was enrolled, randomized into the study, and received study vaccine.

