#### **6.2 Per Protocol (PP):**

The PP Population is a subset of the mITT Population excluding those participants with major protocol violations as determined by the study investigators (Appendix 1).

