#### **6.3 Maternal Immunogenicity Population**

The Maternal Immunogenicity Population is a subset of the mITT Population that includes only pregnant women participants who received study vaccine, provide baseline and post-vaccination Visit 4 blood draws available for analysis within the protocol-defined time frame,

and with no major protocol violations affecting immunogenicity as determined by the study investigators.

The mITT Population is the primary analysis population for the safety and health outcomes analyses, with the PP Population as a confirmatory analysis population. The Immunogenicity Population is the primary analysis population for maternal immunogenicity outcomes (Exploratory Objectives 5); otherwise the mITT Population will be used for the Exploratory Objectives.

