## 8 ANALYSIS OF STUDY OBJECTIVES

### 8.1 Primary Objective

1. To compare the proportions of adverse birth outcomes in pregnant women vaccinated with RIV4 versus IIV4.
  - o *Research hypothesis: The proportion of pregnant women with adverse birth outcomes will be noninferior (not higher – based on the noninferiority margin) after receipt of RIV4 compared to IIV4.*

This objective will be assessed using a one-sided noninferiority test with the alpha level set at 0.025 (1-sided) and a noninferiority margin of 10%.

The null hypothesis assumes that RIV4 is inferior to IIV4 in regards to the proportion of pregnant women with adverse birth outcomes.

$$H_0: RIV4 - IIV4 \geq 0.10 \text{ (10\%)}$$

The alternative hypothesis states that RIV4 is noninferior to IIV4 in regards to the proportion of pregnant women with adverse birth outcomes.

$$H_a: RIV4 - IIV4 < 0.10 \text{ (10\%)}$$

The upper bound of a stratified (by study site) Newcombe binomial confidence interval (Yan and Su 2010) with Cochran-Mantel-Haenszel (CMH) weighting of the difference will be used to make this assessment.

A composite outcome for adverse birth outcome [defined by the occurrence of at least one of the following events: preterm birth, spontaneous abortion, fetal death or neonatal death] will be used as the primary study endpoint.

Definitions for the component of the primary outcome measures are as follows:

- Preterm birth- born alive at less than 37 weeks and 0 days gestation
- Spontaneous abortion (SAB)- pregnancy loss prior to 20 weeks 0 days
- Fetal death- intrauterine death of fetus at or after 20 weeks 0 days
- Neonatal death- infant death within first 28 days of life.

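### SAP Appendix 1 item 1d removes fully treated women from the confirmatory Per Protocol analysis even when their pregnancy outcome is known from records; the primary mITT analysis keeps them

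*SAP*

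**What the plan says.** - SAP Appendix 1, list 1, item d counts as a major violation: "End of participation in study (e.g. loss to follow-up, early termination/withdrawal) prior to end of pregnancy". No exception is written for a woman whose outcome is later obtained.
- SAP 6.2 forms PP by taking mITT and removing women with Appendix 1 violations, as the investigators determine them.
- SAP 6.1: "The mITT Population includes any participant that was enrolled, randomized into the study, and received study vaccine". SAP 6.3 makes mITT primary for safety and health outcomes, "with the PP Population as a confirmatory analysis population".
- Protocol 4.4 asks that every attempt be made to collect the specified data, "including collection of pregnancy outcome/safety data via medical record review for participants who request withdrawal from study interventions/procedures". It adds: "Participants who withdraw from the study after receiving vaccine will not be replaced".
- Protocol 5.1.3 describes the treatment as one dose: "A single administration of both RIV4 and IIV4 comprises intramuscular delivery of 0.5mL total volume of each vaccine for adults". The visit schedule in Protocol 5.1 places vaccination at Visit 1, Day 1.
- SAP 4.1 takes maternal and infant outcomes from medical record review. Protocol 5.1 adds daily screening of the delivery census, requests for records from outside hospitals (Visit 6), and record releases for mother and infant signed at consent (Visit 7).

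**The concern.** A PP analysis is meant to show the result among women who were treated as the protocol intended. Membership of mITT already requires vaccination, and vaccination is the whole treatment. A woman who later stops visits has therefore missed none of it. The other items in list 1 concern eligibility, consent, repeat participation or another product. Only item 1d turns on staying in the study.

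The two documents pull in different directions. The protocol seeks the outcome of a withdrawn woman from her records, and the SAP then removes her from PP even if it is found. Withdrawal comes after randomisation and could follow a reaction or a complication of pregnancy, so it may relate to both vaccine and outcome. If higher-risk RIV4 women were removed more than comparable IIV4 women, the PP difference would move toward noninferiority. PP could then agree with mITT partly because of who was taken out.

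**Working it through.** **Inputs.** SAP 4.3: N = 430, 5% drop-out, 204 evaluable per arm, 15% event rate in both arms. SAP 8.1: margin 10 points, one-sided alpha 0.025. 1:1 allocation gives 430/2 = 215 per arm.

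**1. The plan's own figure.** Evaluable: 430 × 0.95 = 408.5, about 204 per arm. Power by the unpooled normal approximation is Φ(0.10/SE − 1.96), with SE = √(2 × 0.15 × 0.85/n).
- n = 204: SE = 0.03536, 0.10/SE = 2.828, power = Φ(0.868) = 80.7%. The SAP states about 81%, so the figure reproduces. Exact enumeration of the unstratified Newcombe bound gives 80.4%.

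**2. The most power that rewording could recover.** Suppose every woman in the 5% allowance had a known outcome and stayed in PP.
- n = 215: SE = 0.03444, 0.10/SE = 2.904, power = Φ(0.944) = 82.7% (Newcombe 82.6%).
- Gain: 82.7 − 80.7 = 2.0 points at most.

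**3. Shift in one arm's rate.** Let k RIV4 women be excluded with known outcomes and event risk e, and let the women who stay have 15% events. The PP rate is 15.0%. The full rate is ((215 − k) × 0.15 + k × e)/215, so the shift is k(e − 0.15)/215. Both k and e are assumptions: 11 is the whole 5% allowance in one arm, and 5 is about half of it.

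| k | e = 30% | e = 50% |
|---|---|---|
| 5 | 5 × 0.15/215 = 0.35 points | 5 × 0.35/215 = 0.81 points |
| 11 | 11 × 0.15/215 = 0.77 points | 11 × 0.35/215 = 1.79 points |

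**4. Shift in the difference.** The margin applies to RIV4 minus IIV4. If k and e are the same in both arms, each arm shifts by k(e − 0.15)/215 and the two shifts cancel, so the bias is zero.

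**5. Error at the margin, under assumed imbalance.** Take true rates of 25% (RIV4) and 15% (IIV4), with 5% excluded per arm (215 × 0.95 ≈ 204 left). Excluded IIV4 women have 15% events. The PP rate for RIV4 is (0.25 − 0.05r)/0.95, where r is the event rate among the excluded RIV4 women. Type I error is by exact enumeration of the unstratified Newcombe bound.

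| r | Expected PP difference | One-sided type I error |
|---|---|---|
| 25% | 10.0 points | 2.6% |
| 40% | 9.2 points | 4.1% |
| 60% | 8.2 points | 7.1% |

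The first row, where exclusion is unrelated to outcome, matches the 2.6% obtained with all 215 per arm. The other rows require the excluded RIV4 women to be at raised risk while the excluded IIV4 women are not. Nothing in the documents indicates that this will happen.

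**The case against.** A good part of the opposing case stands.

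- **The primary result is not affected.** A reader might infer that the decisive noninferiority test discards these women, or that data gathered under Protocol 4.4 go unused. Neither follows. SAP 6.1 and 6.3 keep every vaccinated woman in the primary mITT population, and PP is the supporting analysis. A marked selection effect in PP could also show as a gap from mITT.
- **The number of such women is not given.** A reader might treat the 5% allowance (about 22 of 430) as women with known outcomes. SAP 4.3 uses it to go from 430 to about 408 evaluable, so it describes women planned as not evaluable. Protocol 4.4 asks for every attempt, which does not guarantee an outcome, and its record-review clause names women who request withdrawal.
- **Larger shifts lack support.** With all 22 in one arm, the formula in step 3 gives 22 × 0.15/215 = 1.5 to 22 × 0.35/215 = 3.6 points. That requires complete imbalance and two to three times the base risk, in a trial where participants and follow-up staff are blinded (SAP 4.5).
- **One route to selection is closed.** Preterm birth, spontaneous abortion and fetal death each end the pregnancy, so a woman who leaves after one of them stays in PP.
- **The terms may differ.** Withdrawal from interventions or procedures (Protocol 4.4) need not be the end of participation (item 1d), and SAP 6.2 leaves violations to the investigators. This weakens any claim that every such woman will be dropped. It does not remove the point: item 1d names withdrawal without qualification, and a confirmatory population should not rest on case-by-case reading.
- **The 28-day component.** The composite includes "Neonatal death- infant death within first 28 days of life", while item 1d stops at the end of pregnancy. A reader might infer that PP should also require known survival to 28 days. It should not. A preterm live birth already meets the composite, so the condition would either drop women whose outcome is already positive, or keep them while dropping term births with unknown survival. Protocol 5.1, Visit 7 already plans contact and record verification at Day 90, including neonatal death.

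**Conclusion.** The point holds for the confirmatory analysis only. As written, item 1d can remove fully treated women whose pregnancy outcomes are known, which is avoidable selection after randomisation. The size cannot be fixed from the documents and is probably small. The RIV4 rate would shift by about 0.35 to 1.8 points if 5 to 11 such women had 30% to 50% risk (assumed) and those who stay had 15%. There is no bias in the difference if withdrawals are alike in number and risk across arms, and at most about 2 points of power are recoverable. The reason to change the rule is that the selection is unnecessary. No material bias has been shown, and the primary mITT conclusion does not depend on it.

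**What to change.** Reword item 1d of SAP Appendix 1, list 1, to:

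> End of participation prior to end of pregnancy with pregnancy outcome (live birth with gestational age, spontaneous abortion or fetal death) not ascertainable from any source, including medical record review.

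A woman who withdraws or is withdrawn after vaccination then stays in PP when her outcome is obtained under Protocol 4.4, and the question of what counts as the end of participation no longer decides membership for her. Do not add a 28-day survival condition to the PP rule.

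The cost is one line of SAP text. The plan already seeks these records, and no visit, sample or clinical procedure changes. Women with no record from any source remain excluded from PP.
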